Prevention of overt
hypothyroidism following
radioactive iodine therapy for
Graves' disease; a novel
protocol with implications for
future studies

NCT# 01950260

February 12, 2015

Prevention of overt hypothyroidism following radioactive iodine therapy for Graves' disease; a novel protocol with implications for future studies

Principal Investigator: [name]

I. Specific Aims

We aim to test the hypothesis that early treatment with levothyroxine after radioactive therapy for Graves' disease will prevent overt hypothyroidism (primary outcome).

II. Background and Significance

The most common method of treating Graves' disease (GD) in the US relies on rendering the patient hypothyroid with the use of radioactive iodine (RAI) ablation of the thyroid gland followed by lifelong replacement with thyroid hormone (levothyroxine). Our current practice is to reevaluate GD patients 2-4 months after their therapy with RAI. At that time their hyperthyroidism is expected to have been resolved, however the majority are clearly hypothyroid at that point. While many are asymptomatic or minimally symptomatic, some are frankly hypothyroid with related troublesome symptoms (cold intolerance, sleepiness, fatigue, weight gain, hoarse voice etc.).

We and others have identified hypothyroidism following treatment of GD as a risk factor for the development of future Graves' ophthalmopathy (GO), a potentially vision-threatening complication of GD¹⁻³. These studies show that development of hypothyroidism increases the risk of developing GO by an average factor of 3.3. Cohort data from centers where early levothyroxine replacement is routinely administered following RAI therapy^{1,4} suggests that this approach can decrease the risk of GO development. In addition, these data show a very low occurrence of hyperthyroidism symptoms that may present when levothyroxine is given prior to documentation of hypothyroidism. Based on these data, the recent publication of guidelines for the treatment of patients with hyperthyroidism⁵ (with Drs. [name] and [name] as task-force chair and member) recommended that hypothyroidism be avoided following RAI therapy for GD. However, no randomized trial has yet been performed to test the impact of preventing hypothyroidism through a precise protocol of early T4 administration on both GO development and QOL, a lapse that our trial intends to correct.

Completion of our current study to test the hypothesis that early initiation of levothyroxine following a precise protocol using small doses of the medication can prevent development of overt hypothyroidism without an increase in rate of symptomatic hyperthyroidism is necessary before we can design our subsequent study. That study will be a larger multi-center investigation testing the hypothesis that prevention of overt hypothyroidism after RAI using this (or a refined) protocol can prevent development or worsening of GO and at the same time improve the quality of life of these individuals.

III. Progress Report and Preliminary Studies

This project involves performing a therapeutic trial in patients with GD. I have to date participated in 3 such trials. The first trial⁶ was a placebo-controlled trial that involved administration of octreotide or placebo for therapy of active GO. My participation in that trial included data collection, data analysis and drafting of the final manuscript. The second trial (Clinicaltrials.gov Identifier NCT00595335;PI:[name]) is an ongoing placebo-controlled study that tests the benefit of rituximab in patients with active and moderate-to-severe GO. I was involved in designing the trial and I'm currently enrolling and following patients throughout the trial. The third trial (Clinicaltrials.gov Identifier NCT01171690) is another ongoing study testing the impact of teriparatide on the duration of hospitalization post thyroidectomy, in patients that develop postsurgical hypoparathyroidism. I am the PI in this single arm study with historical controls. We expect to complete patient enrollment by the end of 2014. In addition to these trials we have

just published our retrospective cohort results describing the development of hypothyroidism in patients with GD treated with RAI, and its impact on GO development³. This cohort is very similar to the group of patients that we intend to enroll in the current study. Lastly, I have completed a Masters in Clinical Research and Translational Sciences through the Mayo Clinic CTSA. This training has given me important background in clinical study protocol design to data analysis.

In our review of Mayo Clinic records, the majority (102/195;52%) of patients were overtly hypothyroid by the time of their first evaluation after RAI (Fig.1) and 36% had a TSH value > 20 mIU/L.³ Furthermore, we found that 21% of patients are in reality seen for their first return visit after > 3 months post RAI due to practicalities of scheduling and the lack of a standardized protocol for this process. We found that the prevalence of hyperthyroidism decreased as expected between the 2 groups and dropped below 25% in groups with first follow-up after 6 weeks. We calculated the ratio between euthyroidism and hypothyroidism at each follow-up and found the ration to drop below 1.0, favoring hypothyroidism, starting from follow-up period 8-10 weeks and then to decrease linearly thereafter. It is very likely that the development of hypothyroidism in the latter groups is associated with a significant symptomatic hypothyroidism and decrease in patients' quality of life (QOL).

[figure not shown]

Table 1. Distribution of thyroid status at first biochemical follow-up

Period	Hyperthyroid - N (%)	Euthyroid/Subclinical hyperthyroid - N (%)	Hypothyroid - N (%)	Euthyroid/ Hypothyroid ratio
< 6 weeks	12 (42.9)	15 (53.6)	1 (3.6)	15
6-8 weeks	6 (21.4)	11 (39.3)	11 (39.3)	1
8-10 weeks	5 (10.9)	16 (34.8)	25 (54.4)	0.64
10-12 weeks	3 (9.1)	10 (30.3)	20 (60.6)	0.5
12-16 weeks	2 (4.1)	11 (22.5)	36 (73.5)	0.31
> 16 weeks	2 (18.2)	0 (0)	9 (81.8)	0

We found that hypothyroidism present at the first follow-up visit was strongly associated with GO development or deterioration with OR of 3.3, 95% CI:1.3-8.7,p=0.011 (Fig. 2). A multi-variate analysis was performed and included hypothyroidism status at the first follow-up, the administration of corticosteroids concurrently with RAI, smoking status, fT4 level at baseline, gender, age, 24 hr RAI uptake test results, thyroid size and dose of RAI. The factors that remained independently significant were development of hypothyroidism by the first follow-up visit after RAI therapy (OR=3.6) and preexisting GO (OR=2.8; Table 2).

[figure not shown]

Table 2. GO changes correlated with thyroid status at first biochemical

Parameter	Estimate	Odds Ratio	Lower 95% CI	Upper 95% CI	P value
Hypothyroid at first follow-up (ref. - Hyper/Euthyroid)	1.2	3.32	1.26	8.72	0.015
Preexistent GO	0.91	2.48	1.03	5.99	0.043
Steroid prophylaxis (ref. - No)	-0.29	0.75	0.09	6.15	0.79
Smoker (ref. - Non-smoker)	0.47	1.60	0.59	4.37	0.36
Free thyroxine (per unit increase)	-0.08	0.92	0.75	1.13	0.44

IV. Research Design and Methods

a. Study Design/Overview –The design for this study was developed based upon the findings of our retrospective cohort study described above. We propose a randomized trial with 2 arms, intervention and control, as depicted in Figure 3. The randomization will be done in blocks of 6 patients. In the intervention arm patients will start levothyroxine therapy 4 weeks prior to return evaluation with Mayo Endocrinologist, approximately 4 weeks after RAI therapy. The initial dose of levothyroxine will be 25 mcg/day. It will be increased to 50 mcg/day 2 weeks later and then adjusted at 8 weeks post RAI based on a full face-to-face clinical and biochemical evaluation. At the 8 weeks visit the treating physician can be informed about the randomization status (actual levothyroxine dose received by the patient). This will be done only if requested by the treating physician for optimal clinical care and the information will be delivered through the secretarial staff or the study coordinator, after communication with the research pharmacy. Both the active capsules and the placebo will be provided by Mayo Research Pharmacy, who will also coordinate the randomization process. In the control arm patients will receive placebo capsules and be evaluated for levothyroxine therapy during a full face-to-face evaluation at 8 weeks, following currently accepted clinical practice. Patients in both groups will have blood drawn at 4 and 6 weeks (in Rochester if agreed by the patient or by mail-in kit to maximize the percent of data collection), stored and analyzed at a later time (batch processing for limiting costs) for free thyroxine and TSH. The study

coordinator will follow on this process to ensure that the patients perform these interim studies. Development of hypothyroidism will be assessed using these tests at 4, 6 and 8 weeks using the cutoffs for free thyroxine and TSH values as described previously³. For the 8 weeks visit all patients will be asked to bring their medication bottles and the study coordinator will perform a pill count to assess compliance with the protocol. Final evaluation for both groups will be at 6 months after RAI at which time patients will undergo a phone questionnaire which will assess the rate of recurrence of hyperthyroidism and test the feasibility of screening for changes in GO status over the phone. In both groups a quality of life instrument will be used at baseline, 4, 6 and 8 weeks and at 6 months. We will use the hypothyroid-Health Related Quality of Life (hypothyroid-HRQL)⁷ and also the Thyroid Specific Questionnaire (TSQ)⁸. These questionnaires are disease-specific for hypothyroidism. A major advantage to our study is also their ability to be self-administered. These last 2 interventions will be used to assess the feasibility of using them in the larger, multi-center trial where GO prevention and QOL benefit will be the primary outcomes.

[figure not shown]

Figure 3 – Trial flow chart

b. Study Subjects - Inclusion criteria target all adult patients (ages 18-70 years) with GD who will receive RAI for treatment of GD. We plan to have 60 individuals complete the study. For that up to 90 individuals may need to be screened. Exclusion criteria - Patient with clinically manifest GO will be excluded from the study. We will also exclude patients with recent (<1 yr.) history of arrhythmias or any history of ventricular arrhythmias, those with preexistent cardiomyopathy, those with malnutrition and those with psychiatric history that could get worse if patient remains persistently hyperthyroid. Patients unlikely to return for the planned follow-up visits, to comply with the blood drawing schedule and with the completion of the hypothyroid-HDQL and TQS questionnaires will also be excluded. If a medical examination was performed within the last 4 weeks by an endocrinologist we can discuss the study over the phone. The consent material can be exchanged by mail or fax.

d. Data Collection - The data will be collected prospectively and stored in an electronic database. Baseline assessment will include demographic data, thyroid size, thyroid functional parameters (TSH, T4 and T3 levels), RAI uptake and dose, smoking status and history of therapy with corticosteroids or methimazole (pre and post RAI). The development of hypothyroidism is defined as TSH > 3.0 mIU/L or free thyroxine (fT4) < 0.8 ng/dL. The methodology for thyroid functional parameters will be the currently used clinical assays. We will offer blood collection for all the required samples here in Rochester. For

those patients that are not local the blood drawing will be organized with the help of mail-in kits. This will maximize the likelihood of the tests being completed and the study coordinator will follow with the patients over the phone to ensure that this process will happen.

g. Feasibility and Time Frame - Our own data indicate that every year 150 patients with Graves' hyperthyroidism who are evaluated at Mayo Clinic Rochester by [name], [name] or one of other members of the Endocrinology Division and Thyroid Core Group. This group of physicians collaborates closely on clinical studies and would in all likelihood refer their patients with GD for participation in this study. We would therefore expect to be able to enroll at least 30% of this patients group and complete enrollment in 1.5 years' time. Analysis and drafting of the manuscript will likely take an additional 6 months. Compliance with the study planned follow-up time frame should be acceptable for the vast majority of patients as the protocol remains close to the current standard of care while the early thyroid testing will be done utilizing mail-in kits for patients' convenience.

h. Statistical Considerations

Outcomes:

Primary endpoint:

Incidence of overt hypothyroidism at 8 weeks post RAI (TSH > 3.0 mIU/L or FT4 < 0.8 ng/dL)

Exploratory endpoints:

Quality of Life measured by the hypothyroid-HRQL and the TSQ at 8 weeks and 6 months

Development of GO at 6 months

Safety Endpoints

New development/deterioration of symptoms of hyperthyroidism.

Sample Size

The sample size for this study is based on the incidence of hypothyroidism primary endpoint using an $\alpha=0.10$ (two-sided), $\beta=0.10$. The proportions of participants that develop hypothyroidism in the placebo and experimental groups are assumed to be 60% and 20%, respectively. A sample size of 30 per group will provide 90% power to detect a difference between the group proportions of 40% using the two-sided Fisher's Exact test.

Primary Endpoint Analysis:

The difference in the incidence rates of hypothyroidism at 8 weeks will be tested using Fisher's exact test.

Exploratory Endpoint Analysis:

Change in quality of life is measured serial over the course of the study follow-up. Change from baseline will be assessed using a hierarchical linear model ("growth curve"). The primary parameter of interest from the model will be the treatment by time interaction term. Time, for this study, will be a collection of indicator variables representing each assessment point. The incidence of GO will be tested using Fisher's exact test.

Safety Analysis:

Frequency tables of adverse events by treatment groups at the patient level will be tabulated. The relative risk of developing a serious, and at least potentially related, adverse event will be estimated along with the 90% confidence interval for relative risk.

Additional Statistical Considerations

The primary analysis will be conducted according to the intention to treat principle. Efforts will be made to ascertain the incidence of hypothyroidism even in participants that are lost to follow up. In the event the data cannot be obtained, the primary analysis will assume these participants are positive for hypothyroidism. Sensitivity analysis will be conducted on the per protocol data set.

Missing data for the primary endpoint is addressed through the intention to treat analysis. Missing data in exploratory endpoints could occur. The analysis plan for the QOL endpoint include maximum likelihood estimation that allows for missing data, provided the data are missing at least missing at random.

A P-value < 0.10 will be considered significant for the primary endpoint and exploratory analyses.

i. Strengths - The design for this study was developed based upon the findings of our retrospective cohort study described above. This trial design will compare an active intervention with the current practice using the benefit of blinding and randomization for eliminating a placebo effect and differences in known and unknown confounders between the groups. It is also minimally disruptive of patients schedule while providing potential benefit for both quality of life and decreasing the risk of GO. By having the free thyroxine values at 0, 4, 6 and 8 weeks it will provide us with the ability to better predict the development of euthyroidism/hypothyroidism, to decide on the best levothyroxine dose and to adjust the therapeutic sequence accordingly. We have allowed for a low recruiting percentage to avoid the possibility of extending the study beyond the planned funded time frame.

j. Limitations - There may be patients that will report increase/recurrence of hyperthyroidism-like symptoms. Those cases are rare and in the literature early T4 therapy (started at 50 mcg daily 2 weeks after RAI) required discontinuation due to symptoms of thyrotoxicosis in only 7/314 patients (2.2%)^{1,4}. In that case we will decrease the dose of levothyroxine x 2 weeks and if the symptoms persist the medication will be discontinued. Beta-blockers will be used liberally at the discretion of the treating physician.

k. Regulatory aspects – We have discussed extensively and consulted with the Office of Research Regulatory Support on the issue of applicability for an IND application. The intention of the study is to treat with levothyroxine patients that are in the very early stages of developing hypothyroidism. The timing of the therapy is based on data that documents onset of hypothyroidism well before the usual 8-12 weeks follow-up. We have proposed to start at a very conservative dose (25 mcg) which represents 25% of the median dose used in the therapy of hypothyroidism. This is quite safe as mentioned above, with only 2.2% of patients required discontinuation of therapy in similar studies in Europe. In addition the patients will be evaluated 4 weeks later and the dose adjusted as clinically indicated. Given all these considerations we have concluded that we are not outside of the scope of the FDA-approved indication for levothyroxine in hypothyroidism management and we have decided against submitting an IND application.

Table 3 – Schedule of Events

Schedule of Events					

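### Minor: one fixed, printed block size of 6, with week 8 disclosure on request during open enrolment, makes a few allocations partly predictable; varying, pharmacy-held block sizes would reduce this at no cost

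*Combined protocol and SAP*

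**What the plan says.** Section IV.a gives the allocation method in one sentence: "The randomization will be done in blocks of 6 patients". It mentions no variation in size, no strata and no plan to withhold the size. The Research Pharmacy supplies the active and placebo capsules and is the party "who will also coordinate the randomization process".

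The same section permits disclosure of individual arms: "At the 8 weeks visit the treating physician can be informed about the randomization status". It sets a condition, "This will be done only if requested by the treating physician for optimal clinical care", and a route: "the information will be delivered through the secretarial staff or the study coordinator, after communication with the research pharmacy".

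Section IV.g expects to enrol at least 30% of about 150 patients a year and to finish in 1.5 years. It says that the division's physicians "would in all likelihood refer their patients with GD for participation in this study". Section IV.b includes an exclusion that calls for judgement: "Patients unlikely to return for the planned follow-up visits". Table 3 places consent at week 0 and first study drug at week 4. The documents do not say when the allocation itself is drawn.

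**The concern.** Concealment of allocation depends on those who recruit being unable to guess the next arm. In a block of 6, each arm appears exactly three times. Once some arms in an unfinished block are known and unbalanced, the remaining slots are no longer 50:50. Here the block size is in the protocol, arms can become known from week 8 while recruitment continues, and the week 8 physicians and the referring physicians probably overlap, although this is not stated patient by patient. The eligibility judgement about likely return offers a point at which a guess could influence who enters. With 30 patients per group, a few selected patients could disturb the balance that section IV.i relies on randomisation to provide.

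**Working it through.** **Inputs from the documents.** Block size 6; disclosure possible from week 8 (IV.a). Accrual (IV.g and IV.b): 60 patients / 1.5 years = 40 a year, or 150 × 0.30 = 45 a year. Dividing by 52.18 weeks gives 0.767 to 0.862 patients per week.

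**Assumptions, because the documents are silent.** The lag from allocation to disclosure is 8 weeks if the list is drawn at week 0, or 4 weeks if drawn at week 4. The share of arms requested is 50% to 100%. Arrivals follow a Poisson process. The guesser knows the order, the block boundaries and every disclosed arm, which is the worst case.

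**The plan's own figure.** Exact power of the two-sided Fisher test with 30 per group, 60% against 20% and alpha 0.10 is 90.9%, which reproduces the stated 90%. The calculation does not involve block size.

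**Is a block still open when its first patient can be disclosed?** A block fills in 6 / 0.862 = 7.0 to 6 / 0.767 = 7.8 weeks. It is still open if at most 4 further patients arrive during the lag.

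| Lag | Expected arrivals | Block still open |
|---|---|---|
| 8 weeks | 6.1 to 6.9 | 27% to 18% |
| 4 weeks | 3.1 to 3.5 | 80% to 74% |

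**How far a slot moves from 50:50.** With a and b arms disclosed in the open block, P(next = A) = (3 − a) / (6 − a − b). One disclosed arm gives 2/5 against 3/5, so 60% is the smallest departure from even odds. A slot becomes certain only when all three places of one arm are disclosed.

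**Simulated trials of 60, fixed blocks of 6, planned accrual.** The ranges span the two accrual rates.

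| Lag | Arms disclosed | Predictable at 60% or more | Correct guesses |
|---|---|---|---|
| 8 weeks | all | 2 to 4 | 50.6% to 50.9% |
| 8 weeks | half | 2 to 3 | 50.3% to 50.6% |
| 4 weeks | all | 14 to 16 | 54.0% to 54.8% |
| 4 weeks | half | 10 to 12 | 52.2% to 52.7% |

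With all arms disclosed, the certain allocations are 0.1% to 0.2% of 60 (about 0.1 patient) at the 8-week lag and 2.0% to 2.7% of 60 (1.2 to 1.6 patients) at the 4-week lag.

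**Which lag applies to consent.** If the list is drawn at week 0, a person deciding on consent knows only arms drawn at least 8 weeks earlier. If it is drawn at week 4, that person is predicting a draw 4 weeks ahead from arms drawn at least 4 weeks back, so the gap is again 8 weeks. The 8-week rows therefore apply to the eligibility judgement in either case. The 4-week rows describe selection between consent and capsule start.

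**Slower accrual.** At half the planned rate (20 a year, an assumption) with all arms disclosed, the 8-week lag gives about 16 of 60 predictable and 54.8% correct guesses. The 4-week lag gives about 26 and 59.4%.

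**Effect of the change** (blocks of 2, 4 and 6 at random, all arms disclosed, planned accrual):

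| Scheme | Predictable, 8-week lag | Predictable, 4-week lag |
|---|---|---|
| Fixed 6 | 2 to 4 | 14 to 16 |
| Varying, sizes known (0.767 per week) | 2.2 | 10.5 |
| Varying, sizes withheld | about 0.5 | 3 to 4 |

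With sizes known, the certain allocations hardly change (0.1 and 1.6 patients). For varying blocks of 4, 6 and 8 with sizes known, correct guesses are 51.1% and 54.7% at the two lags, against 50.9% and 54.8% for fixed blocks of 6.

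**The case against.** The strongest case against is that this is a good-practice preference with no demonstrated harm. Disclosure is an exception, made on request for clinical care. The pharmacy holds the list, the capsules are masked to week 8 and the primary endpoint is biochemical, so the only route to bias is selection before allocation. No effect on bias or type I error has been shown. The guesser assumed above is also hard to find in practice. With five physicians (an assumption) each using only their own patients' arms, correct guesses fall to about 50.2% at the 8-week lag. The coordinator or secretarial staff could pool arms, but nothing says that they decide eligibility. All of this stands, and it is why the point is minor.

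A reader might infer that part of every open block can be predicted. At planned accrual that does not follow: by the time the first patient of a block can be disclosed, the block is already full in 73% to 82% of cases at the 8-week lag. A reader might also infer that 14 to 16 patients could be selected through the eligibility criterion on likely return. That criterion is applied at consent, where the figure is 2 to 4. The larger figure would require dropping a consented patient before capsule start, and the documents give no physician that discretion.

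It is also fair to say that the change moves the average guess rate by only about one point (54.7% to 53.5% at the 4-week lag). Its main effect is to remove the more predictable slots.

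What the objection does not answer is that the documents give no reason for printing a single fixed size. Predictability also rises if recruitment runs behind plan.

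**Conclusion.** The point holds as a minor, cost-free improvement. At planned accrual, predictability at the consent decision is about 2 to 4 of 60 patients at 60% or more, with about 51% correct guesses. That is an upper bound, because it assumes that every arm is disclosed and pooled by one person who knows the block boundaries. The 14 to 16 figure is conditional on a week 4 draw and on selection after consent. The result rests on the assumed lag, request rate and Poisson accrual, and on a likely but unstated overlap between week 8 and referring physicians. The documents do not support a conclusion that concealment fails or that the primary comparison is biased.

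**What to change.** In section IV.a, replace the fixed block of 6 with permuted blocks of randomly varying size (for example 2, 4 and 6). Keep the sizes in a document held only by the Research Pharmacy and not shared with referring physicians, secretarial staff or the coordinator. Varying the sizes without withholding them gives up most of the gain. It would also help to state when the allocation is drawn and to log each disclosure.

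The cost is one line of protocol text and a regenerated list. Sample size, power and the planned Fisher test do not change.

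### Does Fisher's exact test waste so much of the 10% error allowance that another exact test should replace it?

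*Combined protocol and SAP*

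**What the plan says.** Section IV.h, Primary Endpoint Analysis, names one test: "The difference in the incidence rates of hypothyroidism at 8 weeks will be tested using Fisher's exact test". The threshold, under Additional Statistical Considerations, is: "A P-value < 0.10 will be considered significant for the primary endpoint and exploratory analyses".

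Section IV.h, Sample Size, uses two-sided alpha 0.10, beta 0.10, and hypothyroidism rates of 60% on placebo and 20% on levothyroxine. It concludes: "A sample size of 30 per group will provide 90% power to detect a difference between the group proportions of 40" percentage points, by the two-sided Fisher test. Planning and analysis therefore use the same test at the same level.

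Three other statements bear on how many patients enter the test. Section IV.b: "We plan to have 60 individuals complete the study". Section IV.h, on unobtainable outcomes: "In the event the data cannot be obtained, the primary analysis will assume these participants are positive for hypothyroidism". Section IV.a: "The randomization will be done in blocks of 6 patients". The plan gives no number to be randomised, no dropout rate and no allocation ratio.

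**The concern.** Fisher's test conditions on the total number of events. With about 60 patients few p-values are attainable, and the true error usually lies well below the nominal level. Here the sponsor openly accepts a 10% two-sided error, yet at 30 per arm the test spends little more than half of it. Boschloo's test uses Fisher's p-value only to order the tables. It then takes the largest rejection region whose error stays within 10% at every common event rate. It needs no extra patient or measurement.

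If the loss were material, a 60-patient trial would be giving away power. That would matter most if the control rate fell short of 60%. Table 1 in section III makes this plausible: 39.3% were hypothyroid at 6-8 weeks and 54.4% at 8-10 weeks, and the endpoint is read at 8 weeks.

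**Working it through.** **Inputs.** From section IV.h: 30 per arm, rates 0.60 and 0.20, two-sided alpha 0.10, Fisher's test. From Table 1: 54.4% as an alternative control rate. Assumed here, because the plan is silent: 1:1 unstratified allocation, so that blocks of 6 keep the arms within 3 of each other, and 30 to 36 analysed per arm. That gives 37 splits, 7 equal and 30 unequal.

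**Formulas.** Let b(x; n, p) be the binomial probability and R the set of tables (x, y) that reject.
- Size = maximum over a common rate p of the sum over R of b(x; n1, p) × b(y; n2, p).
- Power = sum over R of b(x; n1, 0.60) × b(y; n2, 0.20).
- Fisher: R is all tables with two-sided p < 0.10.
- Boschloo: R is all tables with two-sided Fisher p at or below the largest cut-off that keeps size within 0.10.

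**Step 1: the plan's own figure.** At 30/30 Fisher's power is 90.9%, so the stated 90% is correct. At 29/29 it is 89.6% and at 28/28 it is 89.4%. The chosen size is thus one at which Fisher's test itself reaches 90%.

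**Step 2: size at 30/30.** Fisher's maximum is 5.60%, at a common rate near 0.30. At 0.40, the average of the two planned rates, it is 5.2%. Boschloo's cut-off is a Fisher p of 0.158, with size 9.86% and power 94.5%. The gain is 94.5 − 90.9 = 3.6 points.

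**Step 3: other arm sizes, all outcomes observed, 60% versus 20%.**

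| Control/active | Fisher size | Fisher power | Boschloo power | Gain (points) |
|---|---|---|---|---|
| 30/30 | 5.6% | 90.9% | 94.5% | 3.6 |
| 30/33 | 7.7% | 94.6% | 95.4% | 0.8 |
| 33/33 | 6.4% | 94.0% | 96.2% | 2.2 |
| 36/36 | 7.6% | 96.3% | 97.2% | 0.9 |
| 35/36 | 9.6% | 97.2% | 97.2% | 0.1 |

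Over the 37 splits the gain runs from 0.1 to 3.6 points, with median 0.8. Over the 30 unequal splits the median is 0.4. The reason is visible in the size column: one unequal patient breaks ties among tables, and Fisher's size at the unequal splits is already 7.6% to 9.6%.

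**Step 4: the plan's missing-data rule.** Arms exceed 30 mainly if some patients do not complete, and those without an obtainable outcome count as hypothyroid. With 30 completers per arm and every extra patient counted as an event, the median gain over the same 37 splits is 0.6 points (range 0.0 to 3.7). With 3 missing in each arm Fisher has 90.1% and Boschloo 92.7%; with 6 in each, 90.1% and 90.3%. Fisher falls below 90% in 9 of the 37 splits. It is 84.0% at 30 control and 33 active, and 84.4% at 33/36, where Boschloo also gives 84.4%. The loss there comes from the imputation rule and unequal dropout, not from the choice of test.

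**Step 5: price of the change.** Ordering by the two-sided p-value controls the sum of both tails. In all 30 unequal splits the error in the favourable direction then exceeds 5%, reaching 5.7% at 31/34; Fisher's stays at or below 4.8%. Doubling the smaller one-sided p-value avoids this. That version has a median gain of 0.6 points, and its rejection region contains Fisher's in only 29 of the 37 splits.

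**The case for a change.** The best case for changing is that it is nearly free. Boschloo's size never exceeded 10% in the 37 splits, and its rejection region always contained Fisher's, so no Fisher-significant result would be lost. At the target of 30 per arm Fisher clears 90% by only 0.9 points. If the control rate is 54.4% with 20% still in the active arm, Fisher's power at 30/30 is 81.5% and Boschloo's 87.5%, a gain of 6.0 points. The headline median also depends on the assumed range: it is 1.2 points for 30 to 33 per arm and 2.2 for 28 to 32. It weights all splits equally, although complete blocks favour exact balance.

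These figures stand, and a statistician who chose Boschloo's test at the outset would have chosen well. They do not show a fault in the plan. The 54.4% case is one row of a retrospective table, varies only the control rate, and still leaves Boschloo short of 90%. It questions the planning assumption, which no choice of test repairs; over the 37 splits the median gain in that case is 2.0 points. Nor is the change quite free: it would amend the primary test of a protocol already written, to a less familiar method whose two-sided conventions differ between programs. It would also have to be fixed before outcomes by arm are seen, in a trial where "At the 8 weeks visit the treating physician can be informed about the randomization status".

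**Conclusion.** The concern does not hold. Fisher's test is valid, its power is correctly stated, and the sample size was computed for it, so the unused part of the 10% is already allowed for. What remains is a preference between two valid exact tests. It is worth 3.6 points at exactly 30/30 and, under the assumed splits, typically under one point when arms are larger or unequal.

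This rests on 1:1 unstratified allocation and 30 to 36 analysed per arm, neither of which the plan states. One limit applies: power of at least 90.9% for Fisher in every split checked holds only when all outcomes are observed. Under the rule that counts missing outcomes as hypothyroid, and with more missing in the active arm, it can fall to about 84%, and in the two such splits shown Boschloo's test does not restore 90% either (84.9% at 30/33 and 84.4% at 33/36).
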